**Protocol Title: Pilot, single center, open, trial of
rifaximin in probable Alzheimer's Disease**

NCT Number: NCT03856359

Date: September 6, 2019

Synopsis

Title:	Pilot, single center, open, trial of rifaximin in probable Alzheimer's Disease" version date Sept. 6, 2019
Study Description:	Pilot trial to examine the relationship between rifaximin therapy and change in cognition, serum neuronal markers, ammonia levels and gut microbiota in patients with mild to moderate Probable Alzheimer's Disease.
Objectives:	
Primary Objective: To test if rifaximin treatment in subjects with AD is correlated with improvement in the ADAS-Cog.
 
Secondary Objective: To test if rifaximin treatment is associated with changes in serum amyloid-beta 42, total-tau, Neurofilament light protein markers, serum pro-inflammatory markers, ammonia levels and gut microbiota in AD subjects.

Endpoints:	
Primary Endpoints:
 
Cognitive domain – Alzheimer's Disease Assessment Scale-Cognitive (ADAS-Cog)

Endpoints:	
Primary Safety Endpoints will be Adverse Events
 
Secondary Endpoints:
 
Serum neuronal markers:
 
Neurofilament light (NF-L)Total TauAmyloid-beta 42 
Serum pro-inflammatory markers:
 
Interleukin (IL) 1 betaIL 2IL 4IL 5IL 6IL 8IL 10IL 13Tumor necrosis factor – alpha 
Gut microbiota
 
Serum Ammonia

Study Population:	Mild to moderate severity of Probable Alzheimer's Disease

Phase:	Pilot trial - 2a
Description of senior care facilities Sites/Facilities Enrolling Participants:	Single Site. Duke University Health System and affiliated
Description of Study Intervention:	Subjects will be treated with rifaximin (Xifaxan, Salix Pharmaceuticals, Bridgewater, NJ) 550 mg Orally twice a day for 12 weeks
Study Duration:	Up to 24 months (for recruitment, treatment, data analyses)
Participant Duration:	3 months treatment plus 2 month follow up

Introduction

There is an urgent need to develop novel therapies for Alzheimer's disease (AD). 10% of persons over age 65 and up to 50% over age 85 have dementia, with over 30 million people affected worldwide. The Food and Drug Administration (FDA) has approved cholinesterase inhibitors (Aricept, Exelon, Razadyne), memantine (Namenda), and a drug combining a cholinesterase inhibitor and memantine (Namzaric) to treat the cognitive symptoms of AD. These medications cannot cure AD or stop it from progressing.

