There has been much speculation for decades regarding the cause of Alzheimer's Disease. Two of the many theories are the focus of our research study. The first theory posits that toxic brain concentrations of ammonia play a role in the AD pathophysiology (Seiler, 1993). There have, however, been no published trials of using ammonia lowering medications for the treatment of AD. The second and more recent theory proposes that there is a symbiotic relationship between gut microbiota and brain homeostasis and that this relationship is disrupted in patients with AD, possibly due to an imbalance in the ratio of pro-inflammatory / anti-inflammatory gut microbiota (De-Paula et al, 2018, Cattaneo et al, 2017).

Background

Rifaximin is a virtually non-absorbed antibiotic with the unique properties of lowering blood ammonia levels and altering gut flora. We hypothesize that Rifaximin will improve cognition and function in AD patients by lowering blood ammonia and / or lowering circulatory pro-inflammatory cytokines secreted by harmful gut bacteria.

We will be measuring blood ammonia levels and pro-inflammatory and anti-inflammatory compounds in the blood and analyzing gut microbiota in patients with AD before and after 3 months of Rifaximin therapy. If patients exhibit measurable improvement in cognition and function, we will analyze our data to see if their improvement correlates with a lower blood ammonia level and / or a shift towards anti-inflammatory species in the gut and a similar shift in the blood cytokine panel to favoring anti-inflammatory compounds.

Evidence supporting our hypothesis for this study is presented below.

Ammonia Neurotoxicity

Ammonia is a substrate as well as a product of 16 different enzymatic reactions in the brain. In the healthy brain, ammonia homeostasis is maintained by its combining with glutamate to form non-toxic glutamine via the glutamine synthetase pathway. In the disease state, high brain ammonia levels adversely affect membrane potential, mitochondrial function, astrocyte morphology, energy metabolism, mRNA and protein expression, brain pH, calcium signaling and other cellular functions in the brain (Bosoi et al, 2009).

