**Protocol Title: Pilot, single center, open, trial of rifaximin in
probable Alzheimer's Disease**

NCT Number: NCT03856359

Date: September 6, 2019

Scientific Rationale for Study Design

This is an open label pilot study designed to provide preliminary evidence on the clinical efficacy of rifaximin in improving cognition in AD patients. We will be looking for improvement in test scores, changes in serum levels of neuronal markers and cytokines and changes in gut microbiota following treatment. We will also be collecting data regarding the safety of long-term use of this non-absorbed antibiotic for this disease. This pilot may form the basis for a future larger randomized, double blind controlled study to further test this hypothesis.

Summary statistics will be compiled for mean/SD change from baseline to endpoint on all cognitive, biomarker and microbiome variables. Statistics for cognitive and plasma biomarker tests will be based on nominal p-value of 0.05 given this is a pilot study. We will also examine multiplicity adjusted p-values for correlations between change in cognitive and biomarker/microbiome variables.

Statistical analyses will combined subjects on QD and BID for analyses as this is a pilot study and both doses may impact gut flora. In posthoc analyses we will put dosing as a covariate to examine dose effects.

As such any improvement in cognitive test score and/or significant correlations between cognition and microbiota changes will be viewed as a positive outcome to inform the design of a future larger study.

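### The SAP calls any cognitive improvement, however small, a positive outcome; if mean cognition would not otherwise change, an inert drug earns that label about half the time.

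*SAP*

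**What the plan says.** The primary objective in the Protocol Synopsis is "To test if rifaximin treatment in subjects with AD is correlated with improvement in the ADAS-Cog". The SAP consists of one section, Scientific Rationale for Study Design, and four of its statements bear on this point:

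- It will summarise "mean/SD change from baseline to endpoint on all cognitive, biomarker and microbiome variables".
- On testing: "Statistics for cognitive and plasma biomarker tests will be based on nominal p-value of 0.05 given this is a pilot study".
- On correlations: "We will also examine multiplicity adjusted p-values for correlations between change in cognitive and biomarker/microbiome variables".
- Looking ahead to a larger study, it closes by saying that "any improvement in cognitive test score and/or significant correlations between cognition and microbiota changes will be viewed as a positive outcome to inform the design".

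The Protocol's Background section frames the correlation analysis differently: "If patients exhibit measurable improvement in cognition and function, we will analyze our data to see if their improvement correlates" with lower blood ammonia and/or "a shift towards anti-inflammatory species in the gut". That analysis starts from an observed improvement and has a stated direction.

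Under Study Design, Overall Design, the trial is single-arm and open-label with 10 treated subjects, and ADAS-Cog-11 is given at baseline and 3 months. The same text lists MMSE at screening only, whereas the schedule table under Study Assessment and Procedures also marks it at week 12. MMSE is not a named endpoint.

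**The concern.** The closing sentence is the SAP's only statement of what counts as success, and it is loose in four ways.

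- **No threshold for improvement.** The word significant is attached only to the correlations. The 0.05 level set earlier for cognitive tests is not tied to this sentence.
- **No named score.** The sentence does not restrict itself to ADAS-Cog.
- **The correlation can stand alone and has no sign.** The Background's conditions, improvement first and then a shift in a stated direction, are not carried over. Read literally, worse cognition together with a correlation opposite to the hypothesis would be positive.
- **The significance level for correlations is left open.** Adjusted p-values are an additional item, so the sentence could mean nominal or adjusted significance.

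Without a control arm, nothing separates a drug effect from practice, expectation or the natural course of the disease. The label is meant to inform a larger study, but the SAP does not limit how often an ineffective drug would receive it.

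**Working it through.** The documents state no SD, effect size, power or error rate, so there is no figure of theirs to reproduce.

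**Inputs.** n = 10 treated (Protocol, Overall Design). The following are assumptions: SD of ADAS-Cog change 4 to 6 points; mean change without drug effect from a 2-point worsening to a 2-point gain; cognitive and correlation results independent. Improvement is read as improvement in the group mean.

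**Cognitive limb.** With true mean worsening δ, P(mean improves) = Φ(−δ / (SD/√10)). At δ = 0 this is Φ(0) = 0.500 for any SD. Whole-number scores with exact ties lower it only to 0.48-0.49.

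**Either limb.** With the correlation family held at 5%, P(positive) = 1 − (1 − p) × 0.95. At p = 0.5 this is 1 − 0.475 = 0.525. A simulation of 200,000 trials gave 0.523.

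**What the label tells the reader.** For a true improvement of 0.5 SD, p = Φ(0.5 × √10) = Φ(1.58) = 0.943, and 0.946 with the correlation limb. The likelihood ratio against no change is 0.946/0.525 = 1.80. It cannot exceed 1/0.525 = 1.90.

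**Dependence on drift.** SD/√10 is 1.265 for SD 4 and 1.897 for SD 6. With the 5% correlation family:

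| Mean change without drug effect | P(positive), SD 4 | P(positive), SD 6 |
|---|---|---|
| worse by 2 points | 0.104 | 0.189 |
| worse by 1 | 0.254 | 0.334 |
| worse by 0.5 | 0.379 | 0.426 |
| none | 0.525 | 0.525 |
| better by 0.5 | 0.671 | 0.624 |
| better by 1 | 0.796 | 0.716 |
| better by 2 | 0.946 | 0.861 |

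**Wider readings, no mean change.**

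- If improvement on either ADAS-Cog or MMSE counts, the cognitive limb alone is 3/4 − asin(ρ)/(2π), with ρ the correlation between the two changes. This gives 0.75 at ρ = 0 and 0.627 at ρ = 0.7. Adding the 5% correlation limb gives 0.76 and 0.65.
- If k independent correlations are each judged at nominal 0.05 (ADAS-Cog only), the rate is 1 − 0.5 × 0.95^k: 0.70 for k = 10 and 0.82 for k = 20. Both values of k and the independence are assumptions.

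**Stricter reading, no mean change.** If improvement had to be significant at two-sided 0.05 in the right direction, the rate would be 2.5% on one score, and 1 − 0.975 × 0.95 = 7.4% with the correlation limb.

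**The case against.** - **It is a pilot.** The sentence speaks of informing a larger controlled study; no go/no-go rule or efficacy claim hangs on it. This limits the consequence. But informing that study is the label's whole purpose, and it does that poorly.
- **Zero drift is an assumption.** The Introduction says of approved drugs that "These medications cannot cure AD or stop it from progressing", which points towards decline. If untreated subjects would worsen by 1 point, the bound on the likelihood ratio rises from 1.9 to between 1/0.334 = 3.0 and 1/0.254 = 3.9; for 2 points it is 5.3 to 9.6. The label is then more informative. This stands as a qualification. However, practice and open-label expectation push the other way, and the trial cannot tell which prevails.
- **Improvement may have been meant as significant improvement.** The wording does not say so. If it was meant, it must be written, because the two readings differ twenty-fold on one score (50% against 2.5%).
- **Some of the wider readings are strained.** The sentence on correlations mentions only adjusted p-values, so the 70% and 82% figures rest on the less natural reading. MMSE is not scheduled at the Baseline Visit, so it fits a change-from-baseline analysis badly. Both points are fair, and the conclusion does not rest on those figures.
- **The Protocol already gives a direction.** It does, but the SAP's and/or rule carries over neither the direction nor the condition of prior improvement.

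**Conclusion.** The concern holds. The rule as written does not discriminate well between an active and an inert drug. With 10 subjects and no mean change otherwise, the false-positive rate is 50% on mean ADAS-Cog alone and 52.5% with a correlation family held at 5%. The 50% does not depend on the SD; the 52.5% also assumes that the two limbs are independent.

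The main condition is zero drift, which the documents neither state nor allow to be checked. Over assumed drifts of 2 points either way and an SD of 4 to 6, the rate runs from about 10% to 95%. The design gives no means of locating the trial within that range. This is a wording defect in a pilot and should be fixed before analysis; the data collection is unaffected.

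**What to change.** Delete the sentence that defines a positive outcome. Suggested replacement:

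> The mean ADAS-Cog-11 change from baseline to week 12 will be reported with its two-sided 95% CI as the primary result and as input to the next design. Without a control arm it cannot separate drug effect from practice, expectation or natural course. Cognition-microbiota correlations are exploratory supporting evidence only, in the hypothesised direction, judged on multiplicity-adjusted p-values, for a short list fixed before the laboratory results are examined.

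The list could be the Escherichia/Shigella and Eubacterium rectale measures named in the Protocol's Objectives and Endpoints table. The Background names other taxa, so the choice is the sponsor's.

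If the sponsor wants to keep a label, it should depend on ADAS-Cog-11 alone, with the 95% CI wholly on the improvement side. Its false-positive rate is 2.5% with no mean change. With a practice or expectation gain it is higher: 7-11% for 1 point and 16-29% for 2 points (SD 6 to 4). Its power at n = 10 is 29% for a true 0.5 SD change and reaches 80% only near 1.0 SD. Deletion is therefore the main proposal.

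The change needs SAP wording only, with no new data or visits. The cost is that fewer results can be called positive and the imprecision becomes visible:

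- The CI half-width is 2.262/√10 = 0.72 SD, or 2.9 to 4.3 points for SD 4 to 6.
- A Bonferroni-adjusted correlation needs |r| above about 0.70 for two measures or 0.73 for three, against 0.63 unadjusted.

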This is an open label pilot study in which we will consent up to 25 subjects in order to treat 10 eligible subjects with probable mild to moderate AD. The study is single site and non-randomized. The subjects will be given rifaximin 550 mg orally twice daily for 3 months after evaluation to ensure they have no contraindications. Subjects at risk for drug interactions or tolerability issues may be started and/or maintained on a lower dose of 550 mg once a day. Individuals on concomitant drugs which are contraindicated per the package insert or in the investigators judgment will be excluded. Individuals on concomitant drugs which are not contraindicated but known to elevate blood levels SIGNIFICANTLY OR THOSE WITH MILD AEs (E.G. MILD DIARHEA) WILL receive qd dosing BASED ON CLINICIAN JUDGMENT. Consent, demographics, history, list of current medications, clinical and safety assessments, MMSE and blood tests (CBC, CMP, TSH, B-12 and Folic acid) will be performed at the Screening Visit. Medical history, physical exam, serum neuronal biomarkers and cytokines, serum ammonia level, Adverse Events and cognitive testing (ADAS-Cog-11) will be performed at the Baseline Visit. A stool sample collection kit will also be given to the subject and caregiver at the Baseline Visit, with instructions for use and how to get the sample back to the research coordinator. The stool sample will be obtained prior the subject taking the study drug. Medical history, physical exam, serum neuronal biomarkers and cytokines, serum ammonia level, Adverse Events and cognitive testing (ADAS-Cog-11) will be performed at the 3 month endpoint visit. A stool sample collection kit will also be given to the subject and caregiver at the baseline visit and 3 month Visit with instructions for use and how to get the sample back to the research coordinator. Interim safety checks will occur via phone calls one week after baseline and then every 2 weeks until the 3 month visit, which will then be followed by a 5 month phone call. Caregivers will be instructed to call the research coordinator or the PI ([name] after business hours or on weekends) if any change in stool is noticed at any time during the study. Unscheduled visit/labs may occur if warranted for safety based on clinical judgment. Because of a small risk of developing *C. difficile* up to 2 months following the last administration of rifaximin, the subjects will be followed for an additional 2 months after the 3 month treatment ends. Subjects who terminate early will receive the 3 month assessment at the time of termination.

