15 REFERENCES

16 HOW SUPPLIED/STORAGE AND HANDLING

17 PATIENT COUNSELING INFORMATION

*Sections or subsections omitted from the full prescribing information are not listed

Differences in the treatment effect of those patients not using lactulose concomitantly could not be assessed.

XIFAXAN has not been studied in patients with MELD (Model for End-Stage Liver Disease) scores >25, and only 8.6% of patients in the controlled trial had MELD scores over 19. There is increased systemic exposure in patients with more severe hepatic dysfunction [see *Warnings and Precautions* (5.4), *Use in Specific Populations* (8.7), *Clinical Pharmacology* (12.3)].

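### The SAP lets a cognition–microbiota change correlation count as a positive outcome on its own, although in an all-treated arm it cannot show that rifaximin changed either one, and no test of microbiota change is planned

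*SAP*

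**What the plan says.** The SAP's only definition of success is the last paragraph of *Scientific Rationale for Study Design*. It joins two routes by an and/or. The first is any improvement on the cognitive test; for the second, "significant correlations between cognition and microbiota changes will be viewed as a positive outcome". Because of the and/or, a significant correlation is enough by itself, and no sign is required.

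The same section plans three kinds of analysis:

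- Mean and SD of change for all cognitive, biomarker and microbiome variables.
- Testing: "Statistics for cognitive and plasma biomarker tests will be based on nominal p-value of 0.05 given this is a pilot study". Microbiome variables are not in that sentence.
- Correlations of cognitive change with biomarker and microbiome change, with p-values adjusted for multiplicity. The method, the number of taxa and the coefficient are not given.

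The Protocol differs in two respects. The Synopsis words its secondary objective as a test of association with changes that include "ammonia levels and gut microbiota in AD subjects". The Background plans to "see if their improvement correlates with a lower blood ammonia level and / or a shift towards anti-inflammatory species in the gut", but only if patients first show measurable improvement in cognition and function, and it names the favourable direction.

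On design, *Overall Design* says "we will consent up to 25 subjects in order to treat 10 eligible subjects with probable mild to moderate AD" and "The study is single site and non-randomized". There is no control group.

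**The concern.** A positive outcome in this pilot is meant to inform a larger trial, so it should depend on something the drug could have caused. A correlation between two change scores in treated subjects shows only whether subjects who changed more on one measure also changed more on the other. Illness, diet, other medication and measurement error can all produce that pattern without any drug effect.

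The analysis that should come first, whether the microbiota shifted on average, has no named test or interval. The plan could therefore report a positive outcome on the microbiota pathway without having tested whether rifaximin treatment was followed by a change in the microbiota at all. One pre-named, correctly signed correlation would have the same weakness, so the point is separate from the choice of threshold or the number of taxa.

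**Working it through.** **Inputs from the documents.** n = 10 treated, single arm, nominal 0.05 (sidedness not stated; two-sided assumed). The documents give no SD, effect size, correlation, number of taxa or adjustment method, so those below are assumptions. The plan has no power figure to reproduce.

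**Step 1: a uniform effect drops out.** Write subject i's cognitive change as δ + eᵢ and microbiota change as γ + fᵢ, where δ and γ are the average effects. Pearson's r uses only deviations from the mean, (δ + eᵢ) − (δ + ē) = eᵢ − ē, and likewise for f. Neither δ nor γ remains. Spearman's coefficient uses ranks, which a constant does not alter. In a numerical check on ten simulated pairs, r = 0.769 and rank correlation 0.552 stayed the same after constants were added to both changes.

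**Step 2: critical value.** |r| = t/√(n − 2 + t²) with t(0.975, 8) = 2.306 gives 2.306/√(8 + 5.318) = 0.632. With Bonferroni over 10 taxa (two-sided 0.005, t = 3.833): 3.833/√(8 + 14.69) = 0.805.

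**Step 3: inert drug.** Simulated bivariate normal changes, n = 10, mean change zero in both, with background covariation ρ between the two changes:

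| ρ | One unadjusted test | Bonferroni over 10, per taxon | Any of 10 significant, one taxon related |
|---|---|---|---|
| 0.3 | 13% | 2% | 6% |
| 0.5 | 33% | 8% | 12% |
| 0.6 | 49% | 15% | 19% |

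The last column follows from the one before. With nine unrelated taxa each tested at 0.005, it is 1 − (1 − p) × 0.995⁹, and 0.995⁹ = 0.956. For p = 0.077 this is 1 − 0.923 × 0.956 = 0.12. It would be higher if several taxa covaried with cognition.

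**Step 4: drug that shifts everyone by 1 SD in both measures, ρ = 0.** The paired t-test on either mean change (9 df, noncentrality 1 × √10 = 3.16) has 80% power. The correlation is significant in 5% of trials. At ρ = 0.5 the unadjusted correlation is significant in 33% of trials whether the drug is inert or shifts both measures by 1 SD, so it cannot tell the two apart.

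**Step 5: effects that vary between subjects.** Take individual effects with SD 1 in both measures, correlated at 0.8. The unadjusted correlation is significant in 21% of trials whether the average effect is 0 or 1 SD. It responds to the spread of effects, not to their mean.

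**Step 6: what a paired analysis of microbiota change would give.** At n = 10 and two-sided 0.05, the rejection rate is 5% with no change. Power is 29%, 80% and 99% for standardised changes of 0.5, 1.0 and 1.5.

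**The case against.** Several counter-arguments have force.

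*The correlations are to be adjusted.* This stands, and it changes the size. A reader might take 13%, 33% and 49% as the trial's false-positive rates. The documents do not support that, because the SAP plans adjusted p-values for these correlations. Adjustment limits chance findings where no association exists. It does not remove a real association that the drug did not cause, so the rates shrink without the defect going away.

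*A working drug would not be missed.* A reader might infer that a drug acting alike on everyone would be declared a failure because its correlation is null. Under the and/or, such a trial would probably be positive through cognition, and nothing in the SAP counts a null correlation against the drug.

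*The cognitive route is looser.* If any favourable mean change counts as improvement, an inert drug is positive in about 50% of trials by that route alone. Adding the adjusted correlation route (10 taxa, one at ρ = 0.5) raises this to about 56%; adding a single unadjusted taxon at ρ = 0.5 raises it to 66%. The marginal harm under adjustment is therefore modest.

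*Microbiota change is not ignored.* Correct. It is summarised, and a mean and SD from 10 subjects yield a paired t and a confidence interval. What is missing is a named summary with a planned test or interval. Blood ammonia may already be covered by the plasma biomarker sentence, though the SAP does not list it.

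*Pooling the two dosing frequencies lets the drug itself create a correlation.* Only slightly. With 2, 3 or 5 of 10 subjects assumed to be on once-daily dosing and to have half of a 2-SD effect, the rate rises from 5% to 7–9%.

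*A paired test without a control cannot attribute change to rifaximin either.* True. It does respond to the average change, and it answers the stated objective.

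**Conclusion.** The point holds in this form. One of the two routes to a positive outcome rests on a statistic that carries no information about a uniform average effect. That route omits the condition and direction the Protocol sets for it, and the microbiota objective has no named test or interval.

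For an inert drug, the adjusted correlation would be significant in roughly 2–15% of trials per taxon, or 6–19% for any of 10, at background covariation of 0.3–0.6. The unadjusted single-test range is 13–49%. These figures rest on assumed covariation, 10 taxa, Bonferroni adjustment and normally distributed changes.

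The consequence is a misleading go signal. A reader might infer that an efficacy claim is at risk, but the SAP uses the outcome only to inform a later study, which the Protocol describes as randomized, double blind and controlled. This should be fixed, but it does not invalidate the pilot.

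**What to change.** In the SAP's last paragraph, delete the and/or clause on correlations as a stand-alone route to a positive outcome. Then:

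1. Restore the Protocol's condition and direction. Correlations are examined as exploratory support, with 95% CIs and adjusted p-values, only if cognition shows measurable improvement. Say what counts as measurable, since an inert drug gives a favourable mean half the time. (The Protocol also names function, but its schedule contains no functional scale.)
2. Add a paired analysis of change with a 95% CI for one microbiome summary named in advance, and state that blood ammonia is among the plasma biomarker tests.
3. Call a correlation supportive only if the 95% CI for that marker's mean change excludes zero in the hypothesised direction. Requiring the right direction alone is too weak: an inert drug meets it half the time, so the unadjusted 33% at ρ = 0.5 falls only to about 16%. An inert drug meets the interval condition in 2.5% of trials (half of 5%).
4. State that without a control neither analysis attributes change to rifaximin.

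The cost is SAP wording and a paired analysis of data already being collected. The downside is one fewer way to call the pilot positive.
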